14.8	Protocol deviations.....	52
14.9	Potential benefits	52
14.10	Compensation.....	52
14.11	Age of respondents.....	52
15.0	STUDY TIMELINE	55
16.0	Annex. Selection of cities for the 2023 PWID IBBS	56

LIST OF ACRONYMS AND DEFINITIONS

AIDS	acquired immunodeficiency syndrome - a chronic, potentially life-threatening condition caused by the human immunodeficiency virus
ART	antiretroviral therapy - the use of HIV medicines to treat HIV infection
Behavioral component	survey of behavioral factors by means of a face-to-face interview method - direct communication between the interviewer and the respondent
Biological component	testing of respondents for HIV infection, hepatitis C and syphilis, as well as pre-test and post-test counseling
CDC	Centers for Disease Control and Prevention
DBS	dry blood spot
GAM	UNAIDS Global AIDS Monitoring
HCV	hepatitis C - an infectious disease caused by the hepatitis C virus that primarily affects the liver
HIV	human immunodeficiency virus infection
HTS	HIV testing services - voluntary medical testing of this person for the presence of HIV antibodies
IBBS	Integrated Biological and Behavioral Surveillance – a methodology using cross-sectional surveys with behavioral and biological components that are linked at the respondent level
KI	key informants - representatives of NGOs or private persons with expert knowledge of the survey target group
MOH	Ministry of health of Ukraine
MSM	men who have sex with men
NGO	non-governmental organization - legalized or registered according to the legislation of Ukraine
PLHIV	people living with HIV
PrEP	pre-exposure prophylaxis - an HIV prevention strategy when HIV negative individuals take anti-HIV medications before coming into contact with HIV to reduce their risk of becoming infected
Primary respondents (seeds)	survey participants, recruited by the NGOs according to the criteria set, being the beginning of other responders' recruitment chain
PSE	population size estimation
PWID	people who inject drugs
RDS	respondent-driven sampling
Recruiter	survey participant recruiting other potential responders among the representatives of the survey target group
RITA	The Recent Infection Testing Algorithm - a generic name for a sequence of laboratory methods to distinguish recent HIV infections from HIV infections which have been present for some time
RT	rapid testing
Secondary respondents	survey participants invited by other PWID who have participated in all components of the survey

1.0 SUMMARY

Conceived as a part of second-generation HIV surveillance¹, integrated biological and behavioral surveillance (IBBS), has become a critical element of HIV response in Ukraine. The primary purpose of IBBS is to estimate the burden of HIV disease and HIV-related risk factors, and estimate the coverage of prevention and treatment services for populations at increased risk for HIV. When conducted repeatedly, IBBS allows to evaluate trends in HIV prevalence and other key indicators over time. These data are essential for program planning, implementation, and evaluation.

This protocol describes the methodology of 2023 round of IBBS among people who inject drugs (PWID) in Ukraine. The study is designed as a cross-sectional survey with biological and behavioral components. The survey sample will be recruited using respondent-driven sampling (RDS) approach and will include 5000 participants in 10 cities across Ukraine. Behavioral data will be collected using individual, structured self/interviewer-administered questionnaire. Biological data will be collected using rapid testing algorithms for HIV, hepatitis C and syphilis. Participants with confirmed new positive test results will be referred to health care institutions for follow-up and care. Dry blood spot (DBS) samples will be collected to assess recency of HIV infection and viral load.

[figure not shown]
The survey “Integrated Biological and Behavioral Survey among People Who Inject Drugs” will be conducted in 2023, as a component of a SILTP “Strengthening HIV Treatment, Laboratory Services, Medication Assisted Therapy, and Program Monitoring in Ukraine under the President's Emergency Plan for AIDS Relief (PEPFAR)” implemented by the State Institution “Public Health Center of the Ministry of Health of Ukraine” (the PHC) with the support from the US Centers for Disease Control and Prevention (CDC). (Cooperative agreement number - NU2GGH002375).

¹ https://data.unaids.org/publications/irc-pub01/jc370-2ndgeneration_en.pdf

2.0 BACKGROUND AND RATIONALE

Ukraine has one of the highest burdens of HIV among European countries. In 2011, WHO and UNAIDS estimated that there were 230,000 (95% CI 180,000–310,000) people living with HIV (PLWH) in Ukraine². By 2020, this number increased to a total of 257,000 HIV cases³.

Figure 1. HIV incidence and prevalence among PWID based on 2013-2020 IBBS data

who are HIV-positive³.

The official HIV case registration data confirm the increasing importance of PWID in HIV transmission. While heterosexual mode of transmission has been predominant since 2009, with the absolute number of newly registered cases attributed to injecting drug use (IDU) decreasing from 7105 in 2009 to 3773 in 2018, in 2019 and 2020 there was an increase in new IDU-related cases once again, with 4214 and 5960 cases, respectively. Of all cases officially registered in 2020, sexual transmission

The epidemic continues to be driven by people who inject drugs (PWID). According to the previous IBBS round in 2020, HIV prevalence among PWID was 20.3% (in sampled cities), which was highest among all key populations subgroups (men who have sex with men, Transgender people, sex workers, people who inject drugs, people in prison and detention)⁴, and more than 20 times higher than HIV prevalence in general population (0.9%)⁵. The trend in HIV prevalence and incidence among PWID is shown in Figure 1. Given the estimated size of PWID population of 350,500 in 2017, this translates into a total of around 71000 of PWID

² UNAIDS, Global AIDS Update 2020: Seizing the moment Tackling entrenched inequalities to end epidemics. 2020.

³ Public Health Center of the MoH of Ukraine. HIV infection in Ukraine Informational Bulletin #52 Kyiv2021 [Available from: <https://phc.org.ua/kontrol-zakhvoryuvan/vilsnid/monitoring-i-ocinka/informaciyni-byuleteni-vilsnid>].

⁴ <https://www.theglobalfund.org/en/key-populations/#:~:text=In%20the%20context%20of%20HIV,Transgender%20people%2C%20especially%20transgender%20women>

⁵ Тітар І, Сальников С, Огороднік С, et al. Звіт за результатами Інтегрованого біоповедінкового дослідження 2020 року серед людей, які вживають наркотики ін'єкційним шляхом. Київ: Центр громадського здоров'я МОЗ України, 2021.

accounted for 61.2% and parenteral for 38.1% (Figure 2). At the same time, the proportion of cases

acquired through IDU is underestimated due to wide-spread stigma. In a survey of persons recently diagnosed with HIV, the true proportion of IDU-related cases was underestimated by 1.5 times, with true proportion ranging from 44.0% (according to self-report) to 59.7% (taking into account the presence of antibodies to HCV as a proxy indicator for IDU)⁶.

Harm reduction programs such as needle and syringe exchanges (NSP) are a key HIV prevention strategy among PWID, and Ukraine has achieved the recommended coverage rate⁷ of 60% by 2015 and has been maintaining it since then through a national network of non-government and community-based organizations (Figure 3).

Coverage of another key intervention, Medications for Opioid Use Disorder (MOUD) remains low, with about 18,000 patients receiving it in mid-2022, which is about 7% of the estimated number of people who inject opioids in Ukraine.

Figure 2. Modes of HIV transmission in Ukraine, HIV case registration data 2005-2020

[figure not shown]
[figure not shown]

Figure 3. Coverage of PWID with NSP programmes in Ukraine

IBBS is one of the key components of HIV monitoring and evaluation. It has been conducted in Ukraine since 2003, and on a national scale since 2007. It allows for public health officials to monitor trends in key prevalence indicators, assess coverage with key services, and estimate the population size of key populations.

⁶ Dumchev, K., Kornilova, M., Kulchynska, R., Azarskova, M., & Vitek, C., Improved ascertainment of modes of HIV transmission in Ukraine indicates importance of drug injecting and homosexual risk. *BMC Public Health*, 2020. 20 (1)(1288).

⁷ WHO, UNODC, UNAIDS technical guide for countries to set targets for universal access to HIV prevention, treatment and care for injecting drug users – 2012 revision (p.43) Available from: <https://www.who.int/publications/i/item/978924150437>

3.0 OBJECTIVES

The IBBS among PWID in 2023 is designed to:

- assess HIV, anti-HCV, and syphilis prevalence;
- assess prevalence of HIV-related risk behaviors;
- estimate HIV incidence rate;
- assess HIV viral suppression;
- estimate coverage with HIV prevention, care and treatment services, in particular, HTS;
- assess the level of knowledge about routes of HIV transmission and prevention measures;
- estimate PWID population size;
- assess HIV treatment cascade;
- provide data for modelling, and national/international reporting (for example, UNAIDS Global AIDS Monitoring (GAM));
- develop recommendations for HIV prevention, care and treatment programs and identify future research needed to monitor and respond to the HIV/AIDS epidemic among PWID.

4.0 METHODOLOGY OVERVIEW

4.1 Sampling

The sample will be recruited using Respondent-driven Sampling (RDS) methodology. RDS is a variant of a chain referral sampling method, which was specifically designed to reach “hidden” populations⁸. RDS recruitment starts with some purposefully selected members of the study population referred to as “seeds”. Emphasis is placed on selecting seeds with large social networks and who know people from diverse backgrounds. After enrolling and completing the survey process, each seed is given a specified number of uniquely coded coupons, with which to recruit their peers (i.e., eligible PWID). Recruited peers who agree to enroll and complete the survey steps make up the first wave of participants and are also given uniquely coded coupons with which to recruit their peers. The use of this recruitment strategy produces successive waves of recruitment, ideally long recruitment chains of respondents, and continues until the desired sample size is reached.

The number of involved representatives of the target group allowed to be recruited by each participant is limited to three (persons), allowing for the recruitment to be conducted in various social networks. RDS coupons contain the Study ID of a respondent and are registered in a special programmatic software to track who recruited whom (Annex 9. Survey participant’s coupon). Encrypted QR-codes (electronic coupons) contain information about who and by whom is recruited to participate in the survey. The primary compensation is paid at the first survey visit for the participation in the survey. Secondary compensation is paid at the second survey visit for each person the participant recruits who participates in the survey.

Analysis of RDS data relies on each participant providing their social network size and active monitoring of who recruited whom using the information from the uniquely coded coupons. Use of the unique coupon codes eliminates the need to collect personal identifying information, such as names and addresses, maintaining the anonymity and confidentiality of survey respondents. When conducted and analyzed properly, RDS eliminates biases commonly associated with other chain referral sampling methods, which yields findings representative of the network from which the sample was taken.

4.2 Inclusion and exclusion criteria

Selection criteria and verification methods are described in the table below.

Inclusion criteria	Verification methods
Drug injection within the last 30 days	Self-declaration AND confirmation by healthcare worker (presence of punctures on the participant’s body from injection drug use)
14 years old and older as of the survey period	Self-declaration AND visual control by coupon-manager
Not less than 1 month of residence/work/surveying in the area where	Self-declaration

⁸ Lisa G. Johnston (Tulane University), Keith M. Sabin (UNAIDS), “Sampling hard-to-reach populations with respondent driven sampling”, Methodological Innovations Online (2010), 5(2) 38-48

survey is conducted	
Informed consent to participate in all survey components, namely: (1) questionnaire completion; (2) capillary blood collection with EDTA K3 blood micro containers (microtainers) for further rapid testing for HIV, hepatitis C and syphilis; second HIV diagnostic rapid testing in case of positive results; dry blood spot (DBS) for further testing to detect recent HIV infection and viral load level	Signed informed consent to participate in the survey

Exclusion criteria	Verification methods
Repeated participation in one survey round	Self-declaration OR visual identification of a repeated attempt by coupon-manager
Refusal to participate in one or several survey components	Absence of signed informed consent to participate in the survey
Alcohol or drugs intoxication, which does not allow to understand and answer questions of the questionnaire, and the respondent's behavior threatens his own safety or the safety of others	Visual control by coupon-manager

4.3 Selection of sites

Available recommendations suggest to perform sample size calculation based on indicators with lowest effective sample size (e.g., viral suppression, where effective sample is limited to the HIV positive fraction). However, with the desired level of precision (e.g. less than +/-10%) at the city level, this yields sample sizes which are not feasible, especially in the cities with low HIV prevalence (e.g. Kharkiv). Therefore, it was recommended to consider clustering of cities based on analyses of trends/similarities to ensure a larger sample size.⁹

Prior to 2020, the IBBS in Ukraine were conducted in each administrative unit (N=27), presumably generating a nationally-representative sample, enabling direct comparison of indicators across rounds and analysis of trends.¹⁰ After the resources for surveillance became more limited, the number of participating cities was decreased to 12 in 2020. The selection of cities was made by the national working group, based on epidemiologic and programmatic priorities. Nevertheless, a direct comparison between 2020 and previous rounds is not possible due to the difference in geography and varying sample sizes in cities that participated in each round.

Considering that accurate monitoring of trends in key indicators in IBBS series is at least as important as point estimates, and also following the CDC recommendation (to cluster cities), it is proposed that *a single cluster of cities will be selected for this round and will remain stable* in the next rounds of IBBS. This strategic approach also corresponds to the concept of sentinel surveillance, in which a consistent sample of sites continues to generate data over an extended period of time. As the sentinel

⁹ CDC/DGHT Key Population Surveillance Team and CDC Ukraine Joint Evaluation of IBBS in Ukraine – Nov. 2017

¹⁰ Dumchev, K., Sazonova, Y., Salyuk, T., & Varetska, O. (2018). Trends in HIV prevalence among people injecting drugs, men having sex with men, and female sex workers in Ukraine. *Int J STD AIDS*, 29(13), 1337-1344.

doi:10.1177/0956462418784096

approach implies, selected sites should represent geographically and epidemiologically diverse areas and be most likely to detect emerging behavioral and epidemiologic trends. Given that, the following cities were selected by the national IBBS working group as **sentinel** sites for the 2023 and future rounds of PWID IBBS in Ukraine:

- **Kyiv (fast track city, capital, northern sub-region, largest PWID population)**
- **Dnipro (fast track city, eastern sub-region, high IDU prevalence)**
- **Odesa (fast track city, southern port city, sensitive to new drug use trends)**
- **Kharkiv (north-eastern sub-region, on drug trafficking route from neighboring country, low HIV prevalence)**
- **Cherkasy (central sub-region, high HIV prevalence)**
- **Lviv (western sub-region, on drug trafficking route to/from EU, sensitive to European trends)**

Key characteristics of the selected cities are presented in the Annex. Selection of cities for the 2023 PWID IBBS **on page 55.**

Given the budget allocation for the 2023 IBBS, additional cities will be selected for participation by the national IBBS working group. Similarly to the 2020 round, the selection will be done by a working group based on programmatic and epidemiologic considerations. Possible reasons for selection include not being included in the recent IBBS rounds, assessment of impact of city-level interventions, evidence of outbreaks or unusual behaviors based on other data sources (e.g. SEM, other studies). For the 2023 round, an important priority will be to assess the situation in cities most affected by the war (previously occupied and/or severely damaged). The following cities will be considered as **additional** sites:

- Vinnitsa. (center, less affected by war, significant inbound migration, not included in the 2020 round). *At a meeting of the IBBS working group (June 16, 2023), Vinnytsia was chosen instead of Kherson (by a vote of IBBS working group members). After the Kakhovka dam on the Dnieper River was damaged by Russians, there're some difficulty to conduct IBBS in Kherson (regional team and participant's safety, other difficulties).*
- Zaporizhzhia (south, near the front line, significant out-migration, not included in the 2020 round)
- Chernihiv (north, heavily damaged, not included in the 2020 round)
- Rivne (west, less affected by war, significant inbound migration, not included in the 2020 round)

4.4 Sample size and power calculation

To calculate the sample size, a design effect was empirically estimated in the 2020 IBBS data set using the Gile's SS estimator based on the actual network size in "RDS" package in R v.4.0.5 (Table).

	HIV prevalence				Viral suppression			
	Est.	95% CI LL	95% CI UL	D.Eff.	Est.	95% CI LL	95% CI UL	D.Eff.
Bila Tserkva	16.1%	10.2%	21.9%	3.11	77.7%	66.6%	88.7%	2.39
Dnipro	26.5%	19.8%	33.2%	2.78	68.8%	54.8%	82.6%	3.56
Ivano-Frankivsk	9.3%	5.8%	12.9%	2.61	89.3%	82.8%	96.4%	1.44
Kirovohrad	10.2%	7.0%	13.4%	1.80	74.2%	61.4%	87.3%	2.70

Kryvyi Rih	21.9%	16.1%	27.7%	2.13	70.6%	59.9%	81.1%	1.72
Kyiv	18.2%	12.9%	23.5%	3.27	86.0%	77.0%	95.0%	2.96
Mariupil	30.5%	25.3%	35.6%	2.11	80.9%	72.7%	89.1%	2.21
Mykolaiv	33.2%	27.5%	38.9%	2.88	76.4%	68.3%	84.4%	2.49
Odessa	21.2%	15.3%	27.1%	2.50	80.7%	73.4%	87.9%	1.31
Kharkiv	7.5%	4.1%	11.0%	2.12	90.9%	91.0%	91.0%	-
Khmelnytskyi	29.7%	23.7%	35.7%	2.47	81.9%	74.3%	89.3%	1.91
Cherkasy	38.4%	31.4%	45.6%	2.43	86.5%	80.1%	93.0%	1.61

As shown, the design effect for HIV prevalence ranges from 1.8 to 3.3, and for viral suppression from 1.3 to 3.6. Therefore, a conservative value of 3.0 is used for the following sample size calculation.

The calculation was made for *the single sentinel cluster* sample, with expected HIV prevalence of 21% and 44% viral suppression (combined weighted estimate using 2020 round data for 5 cities and 2017 data for Lviv). Based on the simple asymptotic CI formula,¹¹ 0.05 probability of type I error, anticipated 5% of missing data, and 14% desired precision level for the viral suppression indicator (e.g. 44±7%), the resulting sample size should be 2914.

[figure not shown]
In order to simplify trend analysis across rounds, the total sample will be distributed evenly across participating cities, yielding a rounded target sample size of 500 in each city. This result corresponds to the standard universal sample size used in the US NHBS-IDU.¹² At the city level, assuming the design effect of 3.0 and 5% of missing data (e.g. incomplete data entry, entry errors), a sample size of 500 will provide ~16% precision for a maximally-conservative estimated prevalence for any indicator – 50% (i.e. 50±8%, the interval will be narrower for proportions closer to extremes, either 0 or 100%).

The same target sample size will be used for each additional city (outside the sentinel cluster).

For the trend analysis, assuming the HIV prevalence of 21%, the total sample (with N=629 living with HIV) will provide 80% power to detect a statistically significant increase in viral suppression from 44% (weighted average in sentinel cities in 2020) to 52% (and higher) in the next round, based on 0.05 probability of type I error (Figure).

¹¹ Appendix I-22: Sample Size Calculator for Survey-based Viral Load Suppression

¹² Centers for Disease Control and Prevention. National HIV Behavioral Surveillance System Round 5: Model Surveillance Protocol. December 11, 2018. Available from: www.cdc.gov/hiv/statistics/systems/nhbs/operations.html

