9.6 Treatment cascade indicators among PWID living with HIV

HIV treatment cascade calculation will include the following indicators:

Cascade indicator	Calculation
PWID living with HIV	The latest available PWID population size estimate will be multiplied by the prevalence of HIV among PWID according to the IBBS 2023 data
Know about their HIV-positive status	The proportion of PWID who self-reported their HIV-positive status during survey (among those who received HIV-positive rapid test result upon survey and agreed to answer questions about their experience of previous HIV-testing). This calculation will be cross-checked with the healthcare worker's forms.
Registered in the HIV clinic	The proportion of PWID who self-reported to be officially registered in the HIV clinic as HIV-positive (among those who received HIV-positive rapid test result upon survey and agreed to answer questions about their experience of previous HIV-testing). This calculation will be checked through the healthcare worker's form.
Receive ART	The proportion of PWID who self-reported receiving ART (among those who received HIV-positive rapid test result upon survey and agreed to answer questions about their experience of previous HIV-testing).

¹³ Dumchev, K., Sazonova, Y., Salyuk, T., & Varetska, O. (2018). Trends in HIV prevalence among people injecting drugs, men having sex with men, and female sex workers in Ukraine. *Int J STD AIDS*, 29(13), 1337-1344.
doi:10.1177/0956462418784096

¹⁴ Kassanjee R, McWalter TA, Bärnighausen T, Welte A. A new general biomarker-based incidence estimator. *Epidemiology*. 2012 Sep;23(5):721-8. doi: 10.1097/EDE.0b013e3182576c07.

	testing). This calculation will be checked through the healthcare worker's form.
HIV viral suppression	Results of viral load testing carried out at the stage of laboratory analysis.

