16.0 Annex. Selection of cities for the 2023 PWID IBBS

Region	City	PWID population 2017	HIV prevalence 2020	Viral suppression 2020	Number of IBBS rounds participated 2007-2020	Selection for the 2023 round
AR Crimea	Simferopol				6	
Vinnytsia	Vinnytsia	5400			5	
Volyn	Lutsk	1800			6	
Dnipropetrovsk	Dnipro	20100	23.0%	33.0%	8	sentinel
Dnipropetrovsk	Kryvyi Rih	13300	23.7%	14.1%	4	
Donetsk	Donetsk	11700			6	
Donetsk	Mariupil		29.4%	38.8%	2	
Zhytomyr	Zhytomyr	2600			5	
Zakarpattia	Uzhgorod	1400			5	
Zaporizhzhia	Zaporizhzhia	7900			5	additional
Zaporizhzhia	Melitopol	3400			1	
Ivano-Frankivsk	Ivano-Frankivsk	2000	10.8%	61.5%	6	
Kyiv	Bila Tserkva	2700	15.9%	43.3%	5	
Kyiv	Vasylkiv	1300			3	
Kyiv	Fastiv	1200			3	
Kirovohrad	Kropyvnytskyi	5900	11.9%	28.4%	7	
Lugansk	Lugansk				5	
Lugansk	Sieverodonetsk	900			2	
Lviv	Lviv	6400			5	sentinel
Mykolaiv	Mykolaiv	8500	27.3%	56.4%	8	
Odesa	Odesa	21700	20.4%	42.1%	7	sentinel
Poltava	Poltava	4300			6	
Rivne	Rivne	3500			5	additional
Sumy	Sumy	7800			6	
Ternopil	Ternopil	3200			5	
Kharkiv	Kharkiv	9900	7.1%	20.0%	7	sentinel
Kherson	Kherson	4500			6	additional
Khmelnytskyi	Khmelnytskyi	5200	27.5%	53.2%	6	
Cherkasy	Cherkasy	4600	34.6%	62.1%	8	sentinel
Chernivtsi	Chernivtsi	3700			5	
Chernihiv	Chernihiv	4400			5	additional
Kyiv City	Kyiv City	33700	16.6%	39.6%	8	sentinel
Sevastopol	Sevastopol	6600			4

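### The protocol prints two unreconciled sets of 2020 viral-suppression figures for the same cities, and the 44% used for planning and as the trend baseline cannot come from the section 4.4 table printed above it

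*Protocol*

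**What the plan says.** The section 4.4 table reports 2020 estimates and design effects by city, obtained with Gile's successive sampling estimator. For Dnipro it reads "Dnipro 26.5% 19.8% 33.2% 2.78 68.8% 54.8% 82.6% 3.56", that is, HIV prevalence 26.5% and viral suppression 68.8% (54.8-82.6), with a design effect of 3.56 for the latter. After citing the design-effect ranges for HIV prevalence (1.8-3.3) and viral suppression (1.3-3.6), the section says that "a conservative value of 3.0 is used for the following sample size calculation".

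The sizing paragraph then works "with expected HIV prevalence of 21% and 44% viral suppression (combined weighted estimate using 2020 round data for 5 cities", with 2017 data added for Lviv. It assumes "0.05 probability of type I error, anticipated 5% of missing data" and concludes: "14% desired precision level for the viral suppression indicator (e.g. 44±7%), the resulting sample size should be 2914". The trend paragraph takes 44% again, this time described as a 2020 average, and claims 80% power to detect a rise to 52% with 629 participants living with HIV.

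The Annex on city selection (section 16.0) has its own column for 2020 viral suppression. Its Dnipro row is "Dnipropetrovsk Dnipro 20100 23.0% 33.0% 8 sentinel" and its Kharkiv row is "Kharkiv Kharkiv 9900 7.1% 20.0% 7 sentinel". The last entries before the selection label are HIV prevalence, viral suppression and the number of rounds, so viral suppression is 33.0% and 20.0%.

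Section 9.6 describes the indicator only as "Results of viral load testing carried out at the stage of laboratory analysis".

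**The concern.** Two columns with the same name and year differ by a factor of about two, and the plan draws on both without saying so. The expected proportion agrees with one column, while the viral-suppression design effects printed next to it belong to the other.

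Viral suppression is the indicator that sizes the sentinel cluster, and it is the only one given a powered trend target. Section 4.3 treats trends as at least as important as point estimates. If the starting level is uncertain by some 36 points, an 8-point detectable change cannot be interpreted, and a reader of the 2023 report cannot tell which published 2020 figure is the comparator.

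**Working it through.** **1. The plan's own figures.** Inputs from section 4.4: design effect 3.0, z = 1.96, p = 0.44, half-width 0.07, HIV prevalence 0.21, missing 5%.

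N = 3.0 × 1.96² × 0.44 × 0.56 / 0.07² / 0.21 / 0.95 = 579.5 / 0.21 / 0.95 ≈ 2,905. The stated 2914 is within 0.4%, so it reproduces.

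Power for 44% to 52% with 629 per round, two-sided 0.05 and no design effect: z = (0.08 × √629 − 1.96 × √(2 × 0.48 × 0.52)) / √(0.44 × 0.56 + 0.52 × 0.48) = 0.88, giving 81.1%. The stated 80% reproduces.

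**2. The two sets side by side (2020, %).**

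| City | Prevalence, 4.4 | Prevalence, Annex | Suppression, 4.4 (95% CI) | Suppression, Annex |
|---|---|---|---|---|
| Dnipro | 26.5 | 23.0 | 68.8 (54.8-82.6) | 33.0 |
| Kyiv | 18.2 | 16.6 | 86.0 (77.0-95.0) | 39.6 |
| Odesa | 21.2 | 20.4 | 80.7 (73.4-87.9) | 42.1 |
| Kharkiv | 7.5 | 7.1 | 90.9 (91.0-91.0) | 20.0 |
| Cherkasy | 38.4 | 34.6 | 86.5 (80.1-93.0) | 62.1 |

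Across all 12 cities surveyed in 2020, every Annex suppression value lies below the table's lower 95% limit. The gaps run from 20 points (Mykolaiv) to 71 points (Kharkiv, whose printed interval is degenerate and which has no design effect). The ratio of Annex to table runs from 0.20 (Kryvyi Rih) to 0.74 (Mykolaiv), so it is not a constant rescaling. HIV prevalence behaves differently: the two sources differ by at most 5.9 points, and 11 of the 12 Annex values fall inside the table's interval.

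**3. Which set gives 44%?** Prevalence-weighted mean = Σ(prevalence × suppression) / Σ(prevalence), which is the pooled value under equal city samples.

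- Annex: 4565.9 / 101.7 = 44.9%.
- Section 4.4 table: 9102.6 / 111.8 = 81.4%.

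| Weighting of the five cities | Annex | 4.4 table |
|---|---|---|
| Prevalence | 44.9% | 81.4% |
| Equal | 39.4% | 82.6% |
| PWID population | 37.7% | 81.4% |
| Population × prevalence | 39.8% | 80.0% |

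Lviv's 2017 value is not given, so it was varied from 0% to 100%. With Lviv at 0%, the table's six-city average is still 68.8% (equal weights), 76.0% (population) or 64.2% (prevalence weights, Lviv prevalence assumed 30%: 9102.6 / 141.8). To reach 44% with prevalence weights, Lviv would need zero suppression and a prevalence of about 95% (9102.6 / 44 − 111.8). The Annex reaches 44% readily: its six-city range over Lviv is 32.8-49.5% with equal weights.

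**4. What changes if the table is the indicator meant.**

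- N for ±7 points at p = 0.81: 3.0 × 1.96² × 0.81 × 0.19 / 0.07² / 0.21 / 0.95 ≈ 1,814 (about 1,660-1,890 for 83-80%).
- Half-width with 3,000 (six cities of 500) at p = 0.81: 1.96 × √(3.0 × 0.81 × 0.19 / (3,000 × 0.95 × 0.21)) = 5.4 points. At p = 0.44 it is 6.9 points.
- Detectable rise at 80% power from 80-83%, 629 per round: about 5.6-6.0 points without a design effect, or 9.1-9.8 points with 3.0 (effective n = 629 / 3 ≈ 210).

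**5. What changes if the Annex is the indicator meant.** N stays near 2,905 at a design effect of 3.0, but the viral-suppression design effects then describe other estimates. At p = 0.44, 3,000 participants still give ±7 points up to a design effect of 3.0 × 3,000 / 2,905 ≈ 3.1.

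**The case against.** **Sample size is safe.** At a design effect of 3.0, 44% is close to the worst case: even p = 50% needs only about 2,947, below the planned 3,000. This stands. A reader might infer that the survey is undersized; the figures do not support that.

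**The design effect does not rest on one column.** The value 3.0 was chosen with the HIV-prevalence design effects also in view (up to 3.27), and the discrepancy does not touch those. This stands, so only the viral-suppression part of the justification is in doubt.

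**The trend analysis need not use the printed 44%.** Section 9.4 provides for merging record-level data from earlier rounds, restricted to common cities. A reader might infer that 2023 will show a false rise of some 36 points; that would require bypassing section 9.4. The protection is partial, because the merge is worded as optional and presupposes an indicator definition.

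**The denominator is largely implied.** Section 4.3 limits the indicator's sample to the HIV-positive fraction, section 4.4 uses 629 people living with HIV, and section 8.7 runs viral load on all HIV-positive dried blood spots. This carries weight for 2023, but it does not explain which 2020 column follows that denominator. The only numerical cut-off, 1000 copies/ml in section 8.7, classifies recency, while section 13.1 speaks of undetectable viral load.

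**The cause is unknown.** Calling the sets irreconcilable, or attributing them to different denominators, goes beyond the text. Denominators back-calculated from the table's intervals and design effects (about 152 in Dnipro and 169 in Kyiv) are not smaller than the implied HIV-positive counts (about 123 and 121), so they lend no support to a subgroup reading. One column may simply be wrong.

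**Conclusion.** The protocol contradicts itself on its 2020 viral-suppression figures, and nothing in it explains the difference. The 44% is consistent with the Annex (44.9% prevalence-weighted, 38-40% otherwise) and cannot be obtained from the section 4.4 table (80-83%, and at least about 64% with Lviv at 0% and an assumed Lviv prevalence of up to 30%). The gap between the prevalence-weighted means is 81.4 − 44.9 = 36.5 points, more than four times the 8-point change that the trend scenario targets.

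Three things are therefore unsupported as written: the expected value, the 44% to 52% scenario with its power statement, and the viral-suppression design effects as evidence for 3.0. The arithmetic behind 2914 is sound, and the ±7-point target is met under either set at that design effect. The documents do not show which column is correct. This should be fixed, but it does not invalidate the survey's size or design.

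**What to change.** 1. Reconcile section 4.4 (table, sizing and trend paragraphs), section 9.6 and the Annex. State the denominator, suppression threshold and weighting or estimator once, preferably in section 9.6. The threshold is for the sponsor to choose.
2. Label each viral-suppression column with its definition, or correct the one that is wrong. Explain or replace the Kharkiv row in the section 4.4 table.
3. Re-estimate 2020 viral suppression (and 2017 for Lviv) and its design effect for that one indicator.
4. Restate the expected value, the 2914 with its precision, and the trend baseline with its detectable change. Say whether the design effect enters the power statement (the 80% reproduces only without it), and describe the baseline consistently as including 2017 data for Lviv.
5. In section 9.4, require earlier rounds to be recomputed under the same definition.

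The cost is a re-run of existing data and corrections to text and tables. Recruitment, testing and the target of 500 per city are unaffected.
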